5.5 Subject Follow-Up

Patients will be followed for the duration of active treatment per treatment visit. After end of treatment, patient will be followed every 6 months (+/- 2 months) for survival until withdrawal of consent, death, or

study closure. Patients that discontinue study treatment due to disease progression or toxicity, or experience disease progression after the completion of treatment will remain on study for survival follow up. Patients enrolled to cohort A and B prior to Amendment 14 will remain in survival follow-up until 2 years after the last enrolled patient has completed treatment or autologous HCT. Survival follow up data will be collected by electronic medical records (EMR), telephone, email or public records. Evidence of clinical progression mentioned by patient/family member or documented in EMR need to be reviewed and collected at each timepoint if patient has yet to progress after ending treatment.

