7.2 Dose Delay Criteria for NIVO + ICE

Dose delays for NIVO + ICE are allowed under the following criteria:

- Hematological toxicity: Platelets $\leq 75,000$, Hemoglobin ≤ 8.5 , ANC $\leq 1,500$
- Non-hematological toxicity: All drug-related grade 3/4 AEs. These AEs need to resolve to grade 2 or lower before NIVO + ICE is given.

A delay of up to 14 days is allowed. After 14 days of delay, patients must be taken off the trial.

Filgrastim/packed red blood cells/platelet transfusions are allowed during this period, even during DLT assessment, as ICE therapy itself is supported by these transfusions.

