7.3 Criteria to Resume Treatment

Subjects may resume treatment with study drug when the drug-related AE(s) resolve to Grade ≤ 1 or baseline value, with the following exceptions:

- Subjects may resume treatment in the presence of Grade 2 fatigue
- Subjects who have not experienced a Grade 3 drug-related skin AE may resume treatment in the presence of Grade 2 skin toxicity
- Subjects with baseline Grade 1 AST/ALT or total bilirubin who require dose delays for reasons other than a 2-grade shift in AST/ALT or total bilirubin may resume treatment in the presence of Grade 2 AST/ALT OR total bilirubin
- Subjects with combined Grade 2 AST/ALT AND total bilirubin values meeting discontinuation parameters should have treatment permanently discontinued
- Drug-related pulmonary toxicity, diarrhea, or colitis must have resolved to baseline before treatment is resumed. Subjects with persistent Grade 1 pneumonitis after completion of a steroid taper over at least 1 month may be eligible for retreatment if Investigator allows.
- Drug-related endocrinopathies adequately controlled with only physiologic hormone replacement may resume treatment if Investigator allows.

If the criteria to resume treatment are met, the subject should restart treatment at the next scheduled timepoint per protocol. However, if the treatment is delayed past the next scheduled timepoint per protocol, the next scheduled timepoint will be delayed until dosing resumes.

If treatment is delayed or interrupted for > 6 weeks, the subject must be permanently discontinued from study therapy, except as specified in the discontinuation criteria below.

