ⁱIf feasible, all subjects will undergo biopsy of tumor lesion at the time of disease progression or relapse.

^jOn C1D1, C2D1, C3D1 or any day post-C3D21, but must be prior to AHCT.

^k Tumor measurements will be performed at the same time points indicated for PET-CT scans in footnote f.

^l Includes all patients, regardless of reason for end of protocol therapy; refer to [Section 5.5](#) for follow-up.

^m Optional cycle of NIVO +ICE at the investigator's discretion. PET/CT after Cycle 3, see footnote f.

ⁿ For patients who receive AHCT

^o Refer to [Section 5.5](#) for post-AHCT survival assessments.

^{*}Serum chemistry includes comprehensive metabolic profile: sodium, potassium, chloride, carbon dioxide, glucose, blood urea nitrogen, creatinine, AST, ALT, Alkaline phosphate, total bilirubin, calcium, albumin, total protein, magnesium, phosphate

^{**} Women of childbearing potential must have a negative serum or urine pregnancy test (minimum sensitivity 25 IU/L or equivalent units of HCG) within 24 hours prior to the start of nivolumab.

[†] Must be performed within 10 days of treatment initiation

11 Endpoint Evaluation Criteria/Measurement of Effect

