11.1 Definitions

Evaluable for toxicity: All participants will be evaluable for toxicity from the time of their first treatment with nivolumab.

Evaluable for objective response: Only those participants who have measurable disease present at baseline, have received at least 4 weeks of therapy, and have had their disease re-evaluated will be considered evaluable for response. These participants will have their response classified according to the definitions stated below.

Duration of overall response: The duration of overall response is measured from the time measurement criteria are met for CR or PR, per 2014 Lugano Criteria,¹⁶ (whichever is first recorded) until the first date that relapsed or progressive disease is objectively documented.

Duration of overall CR: The duration of overall CR is measured from the time measurement criteria are first met for CR until the first date that progressive disease is objectively documented.

Duration of stable disease: Stable disease is measured from the start of the treatment until the criteria for progression are met, per 2014 Lugano Criteria,¹⁶ taking as reference the smallest measurements recorded since the treatment started, including the baseline measurements.

Overall Survival (OS): OS is defined as the duration of time from start of treatment to time of death (due to any cause).

Progression-Free Survival (PFS): PFS is defined as the duration of time from start of treatment to time of progression or death, whichever occurs first.

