12.4 Statistical Analysis Plan

In general, data will be summarized by using counts and percents for discrete parameters, and by descriptive statistics (number of observations, mean, standard deviation, median, minimum and maximum) for continuous parameters. Response rates will be calculated as the percent of evaluable patients that have confirmed CR by radiographic response including CT and/or PET scans; 95% Clopper Pearson confidence limits will be calculated for this estimate. Toxicity information recorded will include the type, severity, and the probable association with the study regimen. Tables will be constructed to summarize the observed incidence by severity and type of toxicity. Baseline information (e.g., the extent of prior therapy) and demographic information will be presented as well to describe the patients treated in this study. Time to response and survival endpoints will be estimated using the product-limit method of Kaplan and Meier. The

cumulative incidence of relapse/progression and non-relapse mortality will be calculated as competing risks using the method of Gooley et al¹⁷.

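### Cohort B's CR rate is taken over evaluable patients only, which can leave out early failures that the 35-patient decision rule appears to include; the delay and restart rules for NIVO + ICE also need one clear statement

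*Combined protocol and SAP*

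**What the plan says.** **Denominator.** Section 12.4 states: "Response rates will be calculated as the percent of evaluable patients that have confirmed CR by radiographic response". It attaches 95% Clopper-Pearson limits and does not say which meaning of evaluable applies. Section 11.1 says that only participants with measurable disease at baseline who "have received at least 4 weeks of therapy, and have had their disease re-evaluated will be considered evaluable for response".

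The Cohort B decision rule in Section 12.1.1 has a different base. It plans to enroll and treat 19 to 35 patients, stops at 9 or fewer CRs among the first 19, and calls the regimen worthy of further study at 23 or more CRs after all 35. It has no rule for a missing assessment and no replacement rule.

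In the Cohort B calendar (Section 10.2) the first post-baseline PET-CT falls at the end of week 8. The End of Treatment column has no radiology mark.

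**Delay and restart.** For NIVO + ICE, Section 7.2 permits a delay of up to 14 days and then says "After 14 days of delay, patients must be taken off the trial". On non-hematological events it says "These AEs need to resolve to grade 2 or lower before NIVO + ICE is given". Section 7.3, which names no regimen, says "If treatment is delayed or interrupted for > 6 weeks, the subject must be permanently discontinued from study therapy", apart from exceptions listed in Section 7.5. It also says "Subjects may resume treatment with study drug when the drug-related AE(s) resolve to Grade ≤ 1 or baseline value", with listed exceptions, and requires drug-related pulmonary toxicity, diarrhea or colitis to return to baseline. On study status, where the purpose is to follow survival, Section 5.5 says "Patients that discontinue study treatment due to disease progression or toxicity, or experience disease progression after the completion of treatment will remain on study". Footnote l of the Cohort B calendar says of the End of Treatment column: "Includes all patients, regardless of reason for end of protocol therapy".

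**The concern.** CR rate is one of Cohort B's two primary endpoints. Read together, Sections 11.1 and 12.4 can remove a treated patient from its denominator because treatment failed early: the patient stopped for toxicity, progression or withdrawal (Sections 5.3, 7.2 and 7.5) before four weeks of therapy, or later with no re-evaluation. Such patients are unlikely to be complete responders, so leaving them out can only push the reported rate up.

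The loss is also tied to the other primary endpoint. A patient removed under Section 7.2 because a drug-related, non-hematologic grade 3/4 event has not reached grade 2 after 14 days also meets the definition of unacceptable toxicity in Section 5.2.

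The Section 7.2/7.3 mismatch is a separate, smaller matter. Two sites could manage the same toxicity differently, for example by restarting NIVO + ICE with colitis at grade 2 or waiting for baseline.

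**Working it through.** **1. The plan's own design.** Inputs (Section 12.1.1): n1 = 19, stop if 9 or fewer CRs; N = 35, success if 23 or more; null rate 0.50, target rate 0.74. The exact two-stage binomial is the sum over X1 from 10 to 19 of P(X1) × P(X2 ≥ 23 − X1), with X2 from 16 patients. It gives type I error 0.0444 and power 0.9004. A search for the minimax design returns the same numbers. The sample size is sound; the difficulty lies in the analysis set.

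**2. Who fails the Section 11.1 test.** Cycle 1 lasts 14 days and later cycles 21 days (Section 5.1.5).

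| Event | Day |
|---|---|
| Cycle 2 due | 15 |
| Cycle 3 due | 36 |
| 14-day delay limit reached at Cycle 3 | 36 + 14 = 50 |
| End of Cycle 3, scheduled PET-CT | 14 + 21 + 21 = 56 (end of week 8) |

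- Stops before Cycle 2: has received one 14-day cycle, about 2 weeks of therapy. Read literally, this fails the 4-week condition even if an unscheduled scan shows progression.
- Stops at Cycle 3: has had 14 + 21 = 35 days (5 weeks) and passes the 4-week condition, but reaches the delay limit before the scheduled scan. Evaluable only if disease was re-evaluated in some other way.
- Progression documented after 4 weeks: re-evaluated, so stays in as a non-CR.

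**3. How many early stops to consider.** The documents give no early-stop rate. Section 2.5 reports CR in all 13 Cohort B patients treated so far, so 0 of 13 were lost before assessment. The Clopper-Pearson 95% upper limit is 1 − 0.025^(1/13) = 24.7%. Of the 35 − 13 = 22 patients still to come, that is 0.247 × 22 = 5.4. I take 0 to 5 as the assumed range.

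**4. Effect on the reported rate.** Assume k early stops, all non-CR, and 74% CR in the other new patients: CRs = 13 + round(0.74 × (22 − k)).

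| k | CRs | All treated (95% CI) | Evaluable only (95% CI) | Difference |
|---|---|---|---|---|
| 0 | 13 + 16 = 29 | 29/35 = 82.9% (66.4–93.4) | 29/35 = 82.9% (66.4–93.4) | 0 |
| 3 | 13 + 14 = 27 | 27/35 = 77.1% (59.9–89.6) | 27/32 = 84.4% (67.2–94.7) | 7.2 points |
| 5 | 13 + 13 = 26 | 26/35 = 74.3% (56.7–87.5) | 26/30 = 86.7% (69.3–96.2) | 12.4 points |

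**5. Effect on go/no-go.** With 13 CRs in hand the stage 1 hurdle of 10 is already passed, and 23 − 13 = 10 more are needed. P(at least 10 CRs among 22 − k, at 0.74) is 0.999 for k = 0, 0.988 for k = 3 and 0.950 for k = 5.

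**6. Delay rules side by side.**

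| | Section 7.2 | Section 7.3 |
|---|---|---|
| Stated scope | NIVO + ICE | none stated |
| Delay limit | 14 days | 6 weeks |
| Restart | grade 2 or lower (non-hematological) | grade 1 or lower, or baseline, with exceptions; baseline for pulmonary toxicity, diarrhea, colitis |
| Consequence | off the trial | off study therapy |

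**The case against.** **The rule and the rate might share one denominator.** No text says that the 23-of-35 rule counts an unassessed patient as a non-CR; this is inferred from its being written on treated patients. Section 12.2 speaks of 43 evaluable patients for Cohort A, so one could suppose that Cohort B also runs on evaluable patients, with replacement. That cannot be excluded, but no replacement rule is given. It would not cure the selection either: with a true all-treated CR rate of 50%, and 5% or 10% of patients unassessed and replaced (assumed), type I error would rise from 4.4% to 8.2% or 14.8%.

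**The exclusion is narrow.** Section 11.1 asks for re-evaluation, not a scheduled PET-CT, and progression documented after four weeks keeps the patient in. Toxicity stops are not hidden, since every participant is evaluable for toxicity from the first nivolumab dose. Section 7.5 asks for tumor assessments to continue during dosing interruptions, although not after a permanent stop. All this limits the number affected but does not close the gap. The synopsis definition of evaluable as at least one cycle received would keep these patients in, but it belongs to Cohort A's sample size.

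**Section 7.2 is the specific rule.** Its heading names the combination, and its 14 days and grade 2 match Section 5.2, so they look deliberate; Section 7.5 ends by referring to nivolumab dosing. This largely stands. What remains is that no precedence is stated and Section 7.3 is not confined to nivolumab alone.

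**Stronger readings to avoid.** A reader might infer from Section 7.2 that patients are lost to follow-up. Section 5.5 and footnote l point the other way. A reader might also infer that a failing trial could be reported as a success: 22 CRs fails the rule, yet 22/33 = 66.7% exceeds 23/35 = 65.7%. With 13 CRs already seen this is remote: at 74%, exactly 9 more CRs has probability 0.0008 with no stops and 0.009 with three.

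**Conclusion.** The concern holds for the reported Cohort B primary estimate. Sections 11.1 and 12.4, followed as written, leave out treated patients who stop before four weeks of therapy or without a re-evaluation, and that selection favors the regimen. Under the assumptions in the working, the overstatement is 7.2 points with three early stops, 12.4 points with five (the upper end of what 0 of 13 allows, not an expectation) and nothing with none. The stop counts and the 74% are assumptions. The mismatch with the decision rule rests on an inference about how that rule treats unassessed patients. The documents do not support a claim that the go/no-go decision is in real danger or that the sample size is wrong.

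The Section 7.2/7.3 difference is a secondary point of clarity. It matters most for restarting after pulmonary toxicity, diarrhea or colitis.

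**What to change.** **Sections 12.4 and 11.1.** Define the Cohort B primary CR rate and its Clopper-Pearson interval over all treated patients, counting those without a response assessment as non-CR. Report the rate among Section 11.1 evaluable patients as supportive.

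**Sections 7.2 and 7.3.** State which delay limit and which restart grade apply to NIVO + ICE. Keep the return-to-baseline requirement for drug-related pulmonary toxicity, diarrhea and colitis. Replace the removal from the trial with *discontinued from study therapy and followed per Section 5.5*.

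**Cost.** Amendment wording in four sections, with IRB review. No extra scan or change to the Simon boundaries is needed. The reported rate may be slightly lower. The change would follow 13 known responses, but all 13 are CRs and belong to both denominators, and the all-treated rate can only equal or fall below the evaluable-only rate, so it cannot be seen as favoring the regimen.

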7.3 Criteria to Resume Treatment

Subjects may resume treatment with study drug when the drug-related AE(s) resolve to Grade ≤ 1 or baseline value, with the following exceptions:

- Subjects may resume treatment in the presence of Grade 2 fatigue
- Subjects who have not experienced a Grade 3 drug-related skin AE may resume treatment in the presence of Grade 2 skin toxicity
- Subjects with baseline Grade 1 AST/ALT or total bilirubin who require dose delays for reasons other than a 2-grade shift in AST/ALT or total bilirubin may resume treatment in the presence of Grade 2 AST/ALT OR total bilirubin
- Subjects with combined Grade 2 AST/ALT AND total bilirubin values meeting discontinuation parameters should have treatment permanently discontinued
- Drug-related pulmonary toxicity, diarrhea, or colitis must have resolved to baseline before treatment is resumed. Subjects with persistent Grade 1 pneumonitis after completion of a steroid taper over at least 1 month may be eligible for retreatment if Investigator allows.
- Drug-related endocrinopathies adequately controlled with only physiologic hormone replacement may resume treatment if Investigator allows.

If the criteria to resume treatment are met, the subject should restart treatment at the next scheduled timepoint per protocol. However, if the treatment is delayed past the next scheduled timepoint per protocol, the next scheduled timepoint will be delayed until dosing resumes.

If treatment is delayed or interrupted for > 6 weeks, the subject must be permanently discontinued from study therapy, except as specified in the discontinuation criteria below.

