7.5 Discontinuation Criteria

Treatment should be permanently discontinued for the following:

- Any Grade 2 drug-related uveitis or eye pain or blurred vision that does not respond to topical therapy and does not improve to Grade 1 severity within the re-treatment period OR requires systemic treatment.
- Any Grade 3 non-skin, drug-related adverse event lasting > 7 days, with the following exceptions for drug-related adverse reactions: uveitis, pneumonitis, bronchospasm, hypersensitivity reactions, infusion reactions, and endocrinopathies:
 - Grade 3 drug-related uveitis, pneumonitis, bronchospasm, hypersensitivity reaction, or infusion reaction of any duration requires discontinuation
 - Grade 3 drug-related endocrinopathies adequately controlled with only physiologic hormone replacement do not require discontinuation
- Grade 3 drug-related laboratory abnormalities do not require treatment discontinuation except those noted below
 - Grade 3 drug-related thrombocytopenia > 7 days or associated with bleeding requires discontinuation
 - For patients without liver involvement and without higher AST or ALT levels at baseline, any drug-related liver function test (LFT) abnormality that meets the following criteria requires discontinuation:
 - AST or ALT > 5 x ULN
 - Total bilirubin > 3 x ULN

- For patients with liver involvement (and higher AST or ALT levels at baseline), or those who otherwise have higher AST/ALT levels as allowed in the inclusion criteria, any drug-related liver function test (LFT) abnormality that meets the following criteria requires discontinuation:
 - AST or ALT > 8 x ULN
 - Total bilirubin > 5 x ULN
- Any Grade 4 drug-related adverse event or laboratory abnormality, except for the following events which do not require discontinuation:
 - Isolated Grade 4 amylase or lipase abnormalities that are not associated with symptoms or clinical manifestations of pancreatitis and decrease to < Grade 4 within 1 week of onset.
 - Isolated Grade 4 electrolyte imbalances/abnormalities that are not associated with clinical sequelae and are corrected with supplementation/appropriate management within 72 hours of their onset.
 - Grade 4 lymphopenia or leucopenia.

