- Grade 4 hypophysitis, Grade 3 or 4 adrenal insufficiency, or Grade 4 hyperglycemia. Other Grade 4 drug-related endocrinopathy adverse events, such as ACTH deficiency, hyper- or hypothyroidism, or glucose intolerance other than Grade 4 hyperglycemia, which resolve within 14 days or are adequately controlled with physiologic hormone replacement (corticosteroids, thyroid hormones) or glucose-controlling agents, respectively, may not require discontinuation after discussion with and approval from the Investigator (as allowed by protocol).
- Any dosing interruption lasting > 6 weeks with the following exceptions:
 - Dosing delays or interruptions to allow for prolonged steroid tapers to manage drug-related adverse events are allowed. Prior to re-initiating treatment in a subject with a dosing interruption lasting > 6 weeks, the Investigator must be consulted. Tumor assessments should continue as per protocol even if dosing is interrupted or delayed.
 - Dosing interruptions or delays lasting > 6 weeks that occur for non-drug-related reasons may be allowed if approved by the Investigator. Prior to re-initiating treatment in a subject with a dosing interruption lasting > 6 weeks, the Investigator must be consulted. Tumor assessments should continue as per protocol even if dosing is interrupted.
- Any adverse event, laboratory abnormality, or intercurrent illness which, in the judgment of the Investigator, presents a substantial clinical risk to the subject with continued nivolumab dosing.

8 Agent Information and Risks

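### Two permanent-discontinuation rules in Section 7 are not coherent as printed: one for controlled Grade 3 adrenal insufficiency, one for a combined liver-test rise that has no stated trigger

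*Combined protocol and SAP*

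**What the plan says.** **Adrenal.** Section 7.5 (Discontinuation Criteria) opens with a lead-in under which each main bullet is a reason to stop treatment permanently. Beneath the bullet on prolonged Grade 3 non-skin events it says: "Grade 3 drug-related endocrinopathies adequately controlled with only physiologic hormone replacement do not require discontinuation". Section 7.3 (Criteria to Resume Treatment) likewise lets controlled endocrinopathies resume if the Investigator allows, with no grade limit. Later in 7.5 comes a bullet on Grade 4 events, followed by a short list of events exempt from it. The next line, printed at main level, reads: "Grade 4 hypophysitis, Grade 3 or 4 adrenal insufficiency, or Grade 4 hyperglycemia". That line carries no condition about hormone replacement. It goes on to say that other Grade 4 endocrinopathies may continue if they resolve or are controlled and the Investigator approves.

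**Hepatic.** For some patients with Grade 1 liver tests at baseline, Section 7.3 says they "may resume treatment in the presence of Grade 2 AST/ALT OR total bilirubin". The next bullet treats the joint case differently: "Subjects with combined Grade 2 AST/ALT AND total bilirubin values meeting discontinuation parameters should have treatment permanently discontinued". In 7.5 the liver limits sit below "Grade 3 drug-related laboratory abnormalities do not require treatment discontinuation except those noted below". There, "any drug-related liver function test (LFT) abnormality that meets the following criteria requires discontinuation", and the limits for patients without liver involvement or raised baseline AST/ALT are "AST or ALT > 5 x ULN" and "Total bilirubin > 3 x ULN". For the group with liver involvement or higher baseline AST/ALT they are 8 x and 5 x ULN. Each limit is listed on its own line.

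**The concern.** These rules decide whether a patient is taken off nivolumab for good. Section 6.1 lists adrenal insufficiency, raised AST/ALT and raised bilirubin as expected nivolumab toxicities. Four sites apply the rules, so each should have a single reading.

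The adrenal text appears to exempt a patient in one bullet and stop the same patient in another. The hepatic text makes permanent discontinuation depend on a parameter that the protocol does not supply. The direct stake is safe and uniform handling of these toxicities. A secondary stake is that the tolerability summary would mix patients stopped or continued under different readings.

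**Working it through.** The plan states no figure to reproduce. The check sets the provisions side by side, then bounds the likely number of cases.

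**1. Adrenal: a patient with Grade 3 adrenal insufficiency controlled on physiologic replacement**

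Section 6.1 classes adrenal insufficiency as an endocrine disorder, so the endocrinopathy provisions apply to it.

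| Provision | Result for this patient |
|---|---|
| 7.5, Grade 3 endocrinopathy sentence | Discontinuation not required |
| 7.3, resume rule | May resume if the Investigator allows |
| 7.5, later line, read as a main bullet (as printed) | Permanent discontinuation |
| 7.5, later line, read as an exception to the Grade 4 rule | Discontinuation not required |

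On the printed reading, the first and third rows conflict. On the exception reading that conflict disappears, but two others appear:
- A Grade 3 event needs no exception from a Grade 4 rule.
- The named Grade 4 events would continue unconditionally, while the remaining Grade 4 endocrinopathies would need resolution or control plus Investigator approval.

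The conflict on the printed reading is limited to controlled Grade 3 cases. The exemption does not cover an uncontrolled Grade 3 case or any Grade 4 case.

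**2. Hepatic: a patient whose AST/ALT and bilirubin are both Grade 2**

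Sections 7.1 to 7.5 contain no joint criterion. The documents do not print the CTCAE cut-offs, so both possibilities are taken in turn, reading the limits as separate tests:
- If Grade 2 values stay at or below the single-test limits, as their place under a Grade 3 bullet implies, no limit in 7.5 is met and the 7.3 rule never applies.
- If a Grade 2 value could exceed a single-test limit, 7.5 would already require discontinuation on that test alone, and the joint rule would add nothing.

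Either way, the joint rule has no effect of its own. If the two limit lines are read as one joint criterion, they still sit under the Grade 3 bullet and give no Grade 2 trigger.

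**3. Liver groups in 7.5**

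The first group has neither liver involvement nor raised baseline AST/ALT. The second has liver involvement with raised baseline AST/ALT, or raised AST/ALT otherwise allowed by the inclusion criteria. Section 3.1 sets only upper limits for patients with liver involvement (AST/ALT 5.0 x ULN, bilirubin 3.0 x ULN), so such a patient can enrol with normal AST/ALT. It is then unclear whether 5 x or 8 x applies to AST/ALT, and whether 3 x or 5 x applies to bilirubin.

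**4. Likely number of cases in Cohort B (35 patients)**

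- Adrenal insufficiency is in the uncommon band of Section 6.1 (1/1,000 to below 1/100): 35 × 0.001 = 0.035 to 35 × 0.01 = 0.35 expected cases.
- Increased blood bilirubin is rare (below 1/1,000), and a joint rise cannot be more frequent than its rarer part: below 35 × 0.001 = 0.035.
- Section 6.3 gives abnormal bilirubin in 5% of carboplatin patients with normal baseline values, generally mild: 35 × 0.05 = 1.75. This is a loose ceiling on carboplatin's own contribution, because it counts any abnormality, with or without raised AST/ALT.

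The Section 6.1 bands are for nivolumab monotherapy. They may also count a narrower set of events: rash is rare there but 22% in the phase I Hodgkin trial described in Section 2.2.4. NIVO+ICE rates are not given.

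**The case against.** **The adrenal conflict may be a layout effect.** The text was taken from a PDF, and the line directly follows a nested list, so its indentation could have been lost. This stands as a caution, to be checked against the page layout. It does not settle the rule, because the exception reading has its own faults. If the line is a main bullet, a reader could let the specific adrenal entry override the general endocrinopathy sentence, and the wording about other Grade 4 events fits that reading. The protocol states no such precedence, and 7.3 makes no adrenal exclusion.

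**The hepatic rule is conditional.** A reader might infer that 7.3 and 7.5 give sites opposite orders, or that 7.3 means every joint Grade 2 rise to end treatment. The documents do not support either inference. Section 7.3 stops only patients who meet parameters, and with no parameter stated neither section orders discontinuation.

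**Other rules give cover.** For nivolumab alone, 7.1 delays dosing at drug-related Grade 2 or higher when baseline tests are normal. Section 7.3 then generally requires return to Grade 1 or baseline, and 7.5 has a catch-all for substantial clinical risk. This stands, but the cover is partial. For NIVO+ICE, which follows the single nivolumab cycle in Cohort B, the non-hematological delay rule in 7.2 concerns Grade 3/4 events.

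**The Investigator Brochure may hold a joint criterion.** Section 7.4 refers to hepatic and endocrine algorithms there. That document is not available here, 7.3 does not cite it, and 7.4 says its guidance does not replace medical judgment.

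**The liver groups may be exhaustive.** The parenthesis in the second group can be read as description rather than as a further condition. That is possible, so this point is only an ambiguity.

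**Conclusion.** The point holds as a defect of drafting with a safety bearing. Section 7.5 gives no coherent rule for Grade 3 adrenal insufficiency controlled on replacement. Confidence in a direct contradiction is moderate, because it depends on the bullet level; confidence that the text needs clarifying is high. The joint hepatic rule in 7.3 has no stated trigger. That rests on the absence of any combined parameter in Sections 7.1 to 7.5, not on CTCAE cut-offs. The liver-group gap is secondary.

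The size is small. Few cases are likely, with the caveat on the frequency bands, and no sample size, error rate or decision boundary changes. A reader might infer that the CR result is affected, since each Cohort B patient carries 1/35 = 2.9 percentage points. That is the weight of any patient, and nothing in the documents shows that these rules would change a response outcome.

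**What to change.** Amend Sections 7.3 and 7.5 so that they agree:

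1. State whether the hypophysitis, adrenal insufficiency and hyperglycemia line in 7.5 is a stop criterion or an exception. Align it with the Grade 3 endocrinopathy sentence and with the resume rule in 7.3.
2. Either put into 7.5 the combined AST/ALT and bilirubin parameter to which 7.3 refers, or remove the reference from 7.3. If the parameter is in another document, cite it.
3. Word the two liver groups in 7.5 so that every eligible patient falls into exactly one.

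The sponsor's clinicians choose the content; no threshold or clinical rule is proposed here. The cost is amendment wording, and notice to sites of the clarified rules. No tests are added, because AST, ALT and total bilirubin are already in the serum chemistry of both study calendars.
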